3.1 Study Objectives

The objectives of this study are to evaluate the safety and effectiveness of VOLUMA with Lidocaine for the improvement of volume and aesthetic appearance of the nose in the Chinese population.

3.2 Clinical Hypotheses

The mean volume change in nose area from baseline to Week 24 based on digital analysis of each subject's 3-dimensional (3D) images will be significantly greater in subjects treated with VOLUMA with Lidocaine than in untreated control subjects.

4. Study Design

4.1 Structure

This is a prospective, multicenter, randomized, no-treatment-controlled study. Up to 9 investigational sites will enroll and follow subjects who meet the study criteria.

This trial consists of 2 periods including a Control Period and a Post-control Period. The Control Period is the period from the randomization visit until the primary endpoint visit (24 weeks after the last treatment for the treatment group or randomization for the control group). The main purpose of the Control Period is to compare the primary effectiveness parameter, the volume change of nose area basing on 3D imaging data, between the treatment group and the control group. During the Control Period, subjects randomized to the treatment group will receive treatment and be followed for evaluation of safety and effectiveness. During this period, subjects randomized to the control group will not receive treatment but will be followed for safety and effectiveness evaluations.

The Post-control Period is the period after the primary endpoint visit until the end of the study visit (48 weeks after the last treatment for the treatment group or 24 weeks after the last treatment for the control group). The main purpose of Post-control Period is to collect long-term safety and effectiveness data for the treatment group subjects, and to collect safety and effectiveness data for control group subjects who received treatment. Safety and effectiveness data from the treated control group subjects will be analyzed separately.

4.2 Duration

The study will span a total approximately 96 weeks. Enrollment will take approximately 36 weeks. Each subject's participation will encompass: up to 4 weeks for screening for both treatment group and control group, up to 8 weeks treatment and 48 weeks follow-up (after the last treatment) for the treatment group, and 24 weeks no-treatment follow-up, up to 8 weeks treatment, and 24 weeks follow-up for the control group.

4.3 Treatment Groups and Treatment Regimen

4.3.1 Study Treatment

VOLUMA with Lidocaine.

4.3.2 Control Treatment

No treatment during the 24-week control period. Optional treatment with VOLUMA with Lidocaine during the Post-Control period.

4.3.3 Methods for Blinding

Neither the TI nor the subject will be blinded to treatment.

The Evaluating investigator (EI) will remain blinded to treatment assignment throughout the study. The blinded independent Canfield Scientific technician will be responsible for all 3D digital image analyses which will be used for the effectiveness evaluation.

4.3.4 Touch-up Treatment Criteria

Eight weeks after the initial treatment, the subject and the TI will discuss the results of the initial treatment and determine whether optimal aesthetic improvement of the nose has been achieved. If optimal aesthetic improvement has not been achieved, the TI may perform a touch-up treatment. Moreover, if the injected product volume is less than 0.5 mL during initial treatment, the TI must conduct a touch-up treatment to meet the minimal injected product volume defined by the protocol. Beside the initial treatment and optional touch-up treatment, no additional treatment will be administered during the trial period.

4.4 Permissible and Prohibited Medications/Treatments

4.4.1 Permissible Medications/Treatments

All medications and treatments are permitted with the exception of the restricted medications and treatments described in Section 4.4.2.

After the subject consents to the study, the use of any concomitant medication, prescription or over-the-counter, and other therapy procedures are to be recorded on the subject's electronic case report form (eCRF) at each visit along with the reason the medication/therapy/procedure is taken/administered.

Medication/therapy/procedure considered necessary for the subject's welfare may be given at the discretion of the investigator. If the permissibility of a specific medication/therapy/procedure is in question, please contact Allergan.

4.4.2 Prohibited Medications/Treatments

During the course of this study, the subject may not be enrolled in another investigational study. The subject may not undergo nasal surgery, including cartilage grafts; may not receive facial implants of any biomaterials or filler injections of any kind in the nose area (other than filler injections done as part of this study protocol); may not undergo surgery on the eye area; may not undergo orthodontics operations; may not undergo botulinum toxin injections anywhere in the face; and may not undergo desensitization therapy to HA, streptococcal protein, or lidocaine or other amide-based anesthetic.

The decision to administer a prohibited medication/treatment is done with the safety of the study participant as the primary consideration. When possible, Allergan is to be notified before the prohibited medication/treatment is administered.

4.4.3 Escape Medications

Administration of hyaluronidase must not be performed during this study.

4.4.4 Special Diet or Activities

Within the first 24 hours after treatment, subjects should avoid strenuous exercise, extensive sun or heat exposure, and alcoholic beverages. Exposure to any of the above may cause temporary redness, swelling, and/or itching at the injection site.

After treatment, the subject should avoid unnecessary external compression of the nose that could cause product displacement, indentation, or depression of the dorsal surface where product has been placed. The subject should not sleep face down and should avoid any pressure or trauma to the nasal area, including the use of goggles and sunglasses or reading glasses for 1 week. During this time, the subject is advised not to have a facial massage, enter a sauna or hot spring, receive excessive sun exposure, or go swimming. No phototherapy or laser treatment should be performed for 3 months after the last treatment is administered.

4.5 Treatment Allocation Ratio and Stratification

Subjects will be randomized at a 3:1 ratio either to receive VOLUMA with Lidocaine treatment at the outset of the study (treatment group) or to have treatment delayed by 24 weeks (control group).

5. Study Population

5.1 Number of Subjects

At least 160 subjects will be randomized at up to 9 investigational sites at 3:1 randomization ratio in order to have 120 subjects assigned to the VOLUMA with Lidocaine treatment group and 40 subjects assigned to the no-treatment control group. Approximately 136 subjects, including 102 treated subjects will complete the 48-week visit after last treatment with an anticipated dropout rate of 15%.

5.2 Study Population Characteristics

Subjects will be recruited from a population of healthy Chinese adults who desire aesthetic improvement of the nose.

5.3 Inclusion Criteria

The following are requirements for entry into the study:

1. Male or female, Chinese, at least 18 years of age
2. Is not satisfied with his/her aesthetic appearance due to structural features of his/her nose and assessed as either “dissatisfied” or “very dissatisfied” by using the 5-point NSS
3. Requires a total volume of at least 0.5 mL but not exceeding 3.0 mL of VOLUMA with Lidocaine for initial and touch-up treatment combined, and treatment to the nasal dorsum is mandatory to achieve an aesthetic improvement in the subject’s nose appearance, in the TI’s opinion

4. Has a reasonable treatment goal for aesthetic improvement in nose, in the TI's opinion. Subject and TI have aligned the treatment goals
5. Give written informed consent to authorize the use of health and research study information
6. Be able and willing to follow study instructions, comply with the medication and treatment restrictions described in this protocol, and complete all required study visits

5.4 Exclusion Criteria

The following are criteria for exclusion from participating in the study:

[REDACTED]

3. Has a small, shallow nose such that the volume of filler implant needed to create the desired dorsal height is in excess of the ability of the skin and soft tissue to expand and accommodate the implant

[REDACTED]

[REDACTED]

13. Has active autoimmune disease

[REDACTED]

Approval Date: 22-Sep-2017

[REDACTED]

17. Is on a concurrent regimen of lidocaine or structurally-related local anesthetics (eg, bupivacaine)

[REDACTED]

19. Is on an ongoing regimen of anti-coagulation therapy (eg, warfarin)
20. Within 10 days of undergoing study device injection, is on an ongoing regimen of medications (eg, aspirin or ibuprofen) or other substances (eg, high doses of Vitamin C or Vitamin E or herbal supplements with garlic, ginkgo biloba, or ginseng) known to increase coagulation time, or is currently menstruating (study treatment may be delayed as necessary to accommodate menstrual period cessation and/or anti-coagulation washout interval)
21. Has participated in any clinical trials within 4 weeks prior to signing the informed consent form (ICF) or is planning to participate in another clinical trial during the course of this study
22. Females who are pregnant, nursing, or planning a pregnancy during the course of the study. Females of childbearing potential who have a positive pregnancy test result during screening. Females who intend to breastfeed during the study. Females of childbearing potential who are unwilling to use birth control measures during the full course of the study. Birth control measures include oral contraceptives (stable use for 2 or more cycles prior to screening), intrauterine devices, hormonal injections, hormonal implants, bilateral tube ligation, vasectomy, condom or diaphragm plus either contraceptive sponge, foam, or jelly

[REDACTED]

6. Procedures

6.2 Procedures to be Performed

The procedures to be performed at each visit are described below.

6.2.1 Screening Visit

A subject is considered enrolled when s/he has signed the informed consent in the presence of the investigator or appropriately qualified designee. A unique number assigned to each enrolled subject will serve as the subject identification number on all study documents.

For all consented subjects, the investigator or the assigned site staff will document demographic information (sex, age, race); medical/surgical/cosmetic/dental procedure history; vital signs (height, weight, blood pressure in sitting position, pulse, respiratory rate, temperature); perform blood collection for routine hematology and chemistry; and urine collection for routine urinalysis and urine pregnancy testing for female subjects of childbearing potential. All subjects must have treatment goals aligned with the TI during the screening phase. Subject eligibility will be confirmed prior to randomization. The procedures to be performed at the screening visit are specified in [Table 1](#).

6.2.2 Control Period

6.2.2.1 Randomization Visit – All Subjects

Before randomization, female subjects of childbearing potential (sexually active and not sterile, surgically sterilized, or postmenopausal for at least 1 year) must have a negative urine pregnancy test confirmed on the day of randomization, if the screening pregnancy test was not performed within 7 days of the day of randomization.

All eligible subjects will be randomized at a 3:1 ratio either to receive VOLUMA with Lidocaine treatment at the outset of the study (ie, treatment group) or to be followed in a 24-week “no-treatment” observation period followed by an optional delayed treatment (ie, control group).

Before randomization, 3D digital images of the nose area must be captured for all eligible subjects, which will be used as baseline data for subsequent calculation of the nose volume change and nose aesthetic improvement including dorsal height, dorsal width, nasofrontal angle, nasolabial angle, nasal root height, nasal length, and ala depth. These 3D images must be captured before receiving treatment (treatment group subjects). 3D photos need not be repeated before treatment if study treatment is not administered at the randomization visit. The procedures to be performed during the randomization visit are specified in [Table 2](#).

6.2.2.2 Post-randomization, Treatment(s) and Follow-up – Treatment Group

Vital signs (blood pressure in sitting position, pulse, respiratory rate, and temperature) will be collected for all treatment group subjects prior to treatment.

The treatment group subjects will undergo initial treatment on the same day as randomization. If initial treatment does not occur on the randomization day for these subjects, it must occur within 4 weeks after signing the ICF.

The TI must re-confirm that the treatment goal has been aligned with the subject before performing the initial treatment. The TI will administer treatment with VOLUMA with Lidocaine to enhance the volume and aesthetic appearance of the nose.

Following treatment, the TI will document treatment characteristics, including anesthesia usage, injection site, and injection plane, injection volume, injection ease and product moldability. The TI will use an 11-point scale to assess the ease of injection (0 = difficult, 10 = easy) and the product moldability (0 = stiff, 10 = moldable). Subjects will assess the

procedural pain on an 11-point scale (0 = no pain, 10 = worst pain imaginable) immediately after receiving treatment. The TI must observe the subject for the occurrence of any acute adverse events (AEs), such as vascular embolism, for at least 30 minutes after completing treatment. The TI will document treatment characteristics, and the subject will assess the procedural pain immediately after receiving treatment. The TI must monitor the subject for the occurrence of any acute AEs, such as vascular embolism, for at least 30 minutes after completing treatment.

Injection site responses (ISR) must be recorded daily by the subject using the 56-day post-treatment subject diary starting from the day of treatment (initial and touch-up, if performed) (see example diary in Section 14). If an ISR is ongoing at the end of the 56-day post-treatment subject diary after the last treatment, the TI (or designee) will continue to follow the ongoing ISR to resolution via recommended weekly evaluation and will document the entire course of the ISR on the Ongoing ISR form (ISR type, severity [mild, moderate, or severe] ISR start date and ISR end date. Safety phone calls will occur 3 days after treatment (initial and touch-up, if performed).

During the visit scheduled 8 weeks after initial treatment, before conducting any scheduled actions, the TI must confirm whether the subject needs touch-up treatment after evaluating the initial treatment outcome and getting the subject's agreement. If a touch-up treatment is agreed on, then the Touch-up Treatment Visit and all scheduled procedures will be conducted, if the decision is not to conduct touch-up treatment, then the Week 8 Visit and all scheduled procedures will be conducted. Urine pregnancy testing must be conducted and confirmed as negative before performing touch-up treatment.

For treatment group subjects, routine follow-up visits for safety and effectiveness will occur at Weeks 8, 16, and 24 (primary timepoint) after the last treatment. 3D digital images will be collected, and the 5-point Global Aesthetic Improvement Scale (GAIS) will be assessed separately by the EI (judged live) and the subject (using a mirror) by comparing with pre-treatment (baseline) photos. In addition, the subject (using a mirror) will assess satisfaction with the treatment outcome using the 5-point Nose Satisfaction Scale (NSS) and the subject's willingness to recommend the treatment to a friend. Vital signs will be collected at all visits, and laboratory sample collection for routine hematology, chemistry and urinalysis will be performed at Week 24. The procedures to be performed during the control period are specified in [Table 2](#).

6.2.2.3 Post-randomization, Treatment(s) and Follow-up – Control Group

The control group subjects will undergo 3D imaging and EI assessment of the GAIS at Weeks 8, 16, and 24. The procedures to be performed during the control period are specified in [Table 3](#).

6.2.3 Post-control Period

6.2.3.1 Treatment Group Subjects

For treatment group subjects, routine follow-up visits for safety and effectiveness will occur at Weeks 36 and 48 after the last treatment (initial or touch-up). 3D digital images as well as the GAIS, assessed separately by the EI and the subject, will be performed in addition to the subject assessment of satisfaction with the treatment outcome using the NSS and the subject's willingness to recommend the treatment to a friend. Vital signs will be collected at all visits.

Any treatment group subject who withdraws from the study prior to the Week 48 visit must undergo the procedures scheduled for Week 48 at his/her last on-site visit. A urine pregnancy test must be conducted at study exit or at the time of withdrawal if the subject withdraws from the study prior to the Week 48 visit. The procedures to be performed during the post-control period are specified in [Table 2](#).

6.2.3.2 Control Group Subjects

After completing the Week 24 visit (primary timepoint), all control group subjects have the option to receive initial treatment (no later than 10 days after completing the Week 24 visit) and touch-up treatment (8 weeks after initial treatment). If a subject decides not to receive the optional treatment(s), s/he will be considered as completing the study. If a subject decides to receive the optional treatment(s), the TI must re-confirm that the treatment goal has been aligned with the subject before performing the initial treatment. Prior to treatment (initial and touch-up, if administered), female subjects of childbearing potential must have a confirmed negative urine pregnancy test.

All treatment procedures and safety procedures conducted for the treatment group subjects must be followed. The procedures to be performed during the post-control period are specified in [Table 3](#).

For any control group subjects who withdraw from the study before completing the “no-treatment” control period visit, the scheduled procedures for the Week 24 visit of “no-treatment” period must be conducted at his/her last on-site visit. For any control group subjects who receive treatment and withdraw before completing the Week 24 post-treatment visit, all scheduled procedures for the Week 24 post-treatment visit must be conducted at his/her last on-site visit.

6.3 Instructions for the Subjects

At the screening visit, the TI (or designee) will discuss routine alternative treatments that may be available with any subject who is interested in participating in the study. The available alternative treatments include plastic surgery, autologous fat injection, etc; s/he will counsel the subject regarding his/her treatment goals and the potential benefit and limitations of study treatment. After counseling, if the subject’s expectations are not realistic, the TI (or designee) will not proceed with obtaining the subject’s signature on the ICF and will discontinue the subject from the study.

During each study visit, subjects will be required to remove all jewelry, make-up, and lipstick, to avoid interference with the digital photographs.

Starting from the treatment day, the subject must record any ISRs on the 56-day post-treatment subject diary by following the instructions provided on the diary and by the TI.

For 10 days before and 3 days after study treatment administration, subjects should avoid using a regimen of anti-coagulation, antiplatelet, or thrombolytic medications; nonsteroidal anti-inflammatory drugs; supplements of Vitamin C or E, garlic, ginkgo biloba, or ginseng; or other supplements known to increase coagulation time. These precautions are recommended to reduce the risk of posttreatment bleeding or bruising.

For at least 24 hours after treatment, subjects should avoid strenuous exercise, consumption of alcoholic beverages, and extended exposure to sun or heat to reduce the risk of posttreatment redness, swelling, and/or itching.

After treatment, the subject should avoid unnecessary external compression of the nose that could cause product displacement, indentation, or depression of the dorsal surface where product has been placed. The subject should not sleep face down and should avoid any pressure or trauma to the nasal area, including the use of goggles and sunglasses or reading glasses for 1 week. During this time, the subject is advised not to have a facial massage, enter a sauna or hot spring, receive excessive sun exposure, or go swimming. No phototherapy,

laser treatment, intense pulsed light, radio frequency, dermabrasion, chemical peel, or other ablative or non-ablative procedures should be performed in nose and nose adjacent area during the study period.

Subjects will also be instructed to contact the TI or his/her research staff to report any unexpected symptoms or to ask questions about the study.

6.4 Unscheduled Visits

An unscheduled visit may occur for safety purposes (eg, if the subject needs to obtain information regarding AEs or ISRs). An unscheduled visit may also occur to repeat facial digital images if those obtained at the scheduled visit are poor quality images. Applicable procedures will be performed and recorded on the eCRF.

6.5 Early Discontinuation of Subjects

Each subject reserves the right to withdraw from the study at any time without jeopardy to his/her future medical care. All follow-up procedures scheduled to be performed at the final site visit should be performed at the subject's last site visit. Subjects may also be administratively withdrawn if they do not return for follow-up visits. For any subject who withdraws from the study, the date and reason for withdrawal will be recorded on the eCRF. If a treatment-related AE is ongoing at the time of withdrawal, the TI will attempt to follow the subject until the AE has been resolved or follow-up is no longer possible. The TI shall ask for the subject's permission to follow his/her status/condition outside the study.

Randomized subjects who withdraw before treatment will not be replaced by another subject. The subject number and associated randomization number of the withdrawn subject should not be reassigned to a different subject.

If a subject fails to return for 1 or more scheduled study visits, the TI (or designee) will attempt to contact the subject to determine and document the reason the subject has failed to return and to encourage compliance with the study visit schedule.

At regular intervals, the TI (or designee) will record on the eCRF the reasons for which any subjects are discontinued from the study, including subjects who signed the ICF but do not proceed to randomization.

6.6 Withdrawal Criteria

The subject may withdraw at will at any time for any reason.

If a subject has a positive urine pregnancy test prior to initial treatment, the subject will not be eligible for treatment and will be withdrawn from the study. If a subject has a positive urine pregnancy test after treatment, she will continue all scheduled visit and non-treatment procedures. The pregnancy will be followed as described in Section 10.3. If a subject receives hyaluronidase or dermal fillers in the nose area during the trial, s/he will be withdrawn from the study.

7. Response Measures and Summary of Data Collection Methods

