7.5 Summary of Methods of Data Collection

Electronic data capture will be used to collect study-specific information, such as subject and investigator assessments. Completed eCRFs will be reviewed by the TI or EI as applicable (or designee), and the designated monitor will verify the data. Investigators will provide access to hospital files, medical records, and other source documents containing subject clinical/medical information. Source document verification will be performed.

Treatment and safety assessments will be performed by the TI. The initial treatment and touch-up treatment (if performed) for each subject must be performed by the same TI. The effectiveness assessments for each subject are strongly recommended to be performed by the same EI throughout the study. The blinded independent technician will be responsible for all 3D digital image analyses which will be used as effectiveness assessments. At specified timepoints, subjects will complete questionnaires and 56-day post-treatment subject diary(ies).

After signing the ICF and until exit from the study, any untoward signs or symptoms or other AEs as well as concomitant medications, procedures and therapies of all subjects (treatment and control groups) will be carefully monitored by the TI and documented by either the TI or assigned site staff.

Subjects will complete the paper ISR diaries, and responses will be entered into the clinical database.

Canfield Scientific will be responsible for analyzing 3D digital imaging data by independent, blinded technicians. Sites will save photographs onto supplied electronic media and send the storage device to Canfield Scientific. Alternatively, files containing the facial digital photographs may be directly uploaded to Canfield Scientific from the Canfield Scientific equipment.

8. Statistical Procedures

Allergan developed the statistical design of this trial. A separate statistical analysis plan will be prepared to provide specifications for all analyses. The plan will be finalized and approved prior to clinical database lock.

Descriptive statistics will be presented for key outcome measures. Categorical variables will be summarized with frequency and relative frequency. Continuous variables will be summarized by number of subjects, mean, median, standard deviation, minimum, and maximum. Where appropriate, 2-sided 95% CIs for population mean, or population proportion, will be provided as part of the descriptive summary.

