10.2 Compliance with Protocol

The Principal Investigator and designee are responsible for compliance with the protocol at the investigational site. A representative of Allergan will make frequent contact with the investigator and his/her research staff, and will conduct regular monitoring visits at the site to review subject and device accountability records for compliance with the protocol. Any protocol deviations will be discussed with the investigator upon identification. The use of the data collected for the subject will be discussed to determine if the data are to be included in the analysis. All protocol deviations will be reported to the EC according to the EC's reporting requirements.

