11.3 Procedures for Reporting an AE or ADE

All AEs or ADEs occurring during the study period (beginning with signing the ICF) are to be recorded on the appropriate eCRF. For any treatment-related AE that is ongoing at the exit, the Investigator will attempt to follow the subject until the AE has been resolved or follow-up is no longer possible.

AEs that start after the study follow-up period has ended will be considered outside the scope of the study but will be captured by Product Surveillance.

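### Protocol 6.6 takes a study-treated participant who receives hyaluronidase out of the whole study, so later visits and routine recording of new non-serious AEs stop (cheap improvement, low priority)

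*Protocol*

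**What the plan says.** Protocol 6.6 (Withdrawal Criteria) reads: "If a subject receives hyaluronidase or dermal fillers in the nose area during the trial, s/he will be withdrawn from the study". Section 4.4.2 makes clear that the fillers meant are those given outside the study, and 4.4.3 prohibits hyaluronidase. Sections 4.4.1 and 4.4.2 nevertheless leave room for treatment needed for a participant's welfare or safety, so the event is foreseeable.

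The same section handles pregnancy after treatment differently: "she will continue all scheduled visit and non-treatment procedures".

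After withdrawal, these provisions apply:
- A treatment-group participant who leaves before Week 48 "must undergo the procedures scheduled for Week 48 at his/her last on-site visit" (Protocol 6.2.3.1). Section 6.2.3.2 has the parallel rule for controls.
- Treatment-related AEs already ongoing are followed where possible, and "The TI shall ask for the subject's permission to follow his/her status/condition outside the study" (6.5).
- Ongoing injection site responses are followed to resolution (6.2.2.2), and participants with an SAE or SADE are followed to outcome (11.4).

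AE monitoring is otherwise bounded by study exit: "After signing the ICF and until exit from the study, any untoward signs or symptoms or other AEs" are monitored (7.5), and the table in 11.2 ends collection at the last subject visit. AEs that begin once the follow-up period is over "will be considered outside the scope of the study but will be captured by Product Surveillance" (11.3).

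Protocol 4.1 gives the reason for the later visits: "The main purpose of Post-control Period is to collect long-term safety and effectiveness data for the treatment group subjects".

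**The concern.** Stopping study treatment and leaving the study are separate decisions, and 6.6 makes both at once. A participant who needs hyaluronidase after VOLUMA may well have had a complication or a poor result, and so is among those whose later course is of most interest for long-term safety. Under 6.6 that person leaves early. At stake are visit-based safety and outcome data on a few informative participants.

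There is also a small analytic side. The primary MMRM assumes that data are missing at random (SAP 5.3.2). A participant whose volume fell after hyaluronidase and who then exits is modelled as if the volume had followed the rest of the treated group.

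**Working it through.** **1. What continues and what stops after exit**

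| Item | After withdrawal under 6.6 | Source |
|---|---|---|
| Final-visit procedures | Done once, at the last visit | 6.2.3.1, 6.2.3.2, 6.5 |
| Treatment-related AE already ongoing | Followed where possible | 6.5, 11.3 |
| Ongoing injection site response | Followed to resolution | 6.2.2.2 |
| SAE/SADE | Followed to outcome | 11.4 |
| Status outside the study | By permission | 6.5 |
| Remaining scheduled visits | Stop | 6.6 |
| New non-serious AEs, routine recording | Stop; Product Surveillance if exit ends the follow-up period | 7.5, 11.2, 11.3 |

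**2. Follow-up lost**

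Days are counted from the last treatment, with targets of Day 169 (Week 24) and Day 337 (Week 48) from SAP Tables 6-3 and 6-5. The event days are illustrative. The results are upper limits, because 6.5 continues some follow-up.
- Treatment group, Day 7: (337 − 7)/7 = 47.1 weeks.
- Treatment group, Day 60: (337 − 60)/7 = 39.6 weeks. Weeks 16, 24, 36 and 48 are replaced by one exit visit.
- Treatment group, Day 169: (337 − 169)/7 = 24.0 weeks.
- Control after optional treatment, Day 60: (169 − 60)/7 = 15.6 weeks.

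Planned treatment-group follow-up is 120 × 48 = 5,760 person-weeks, so one Day 60 event is at most 39.6/5,760 = 0.7%. With no event rate in the documents, no total can be given.

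**3. Effect on the primary estimate**

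The plan's own figure first: 90 versus 30, difference 0.9 mL, SD 0.9 mL, two-sided 5% t-test. Exact power is 99.7%; the plan states 99.6%. Completers after 15% attrition are 120 × 0.85 = 102 treated and 160 × 0.85 = 136 in total, which leaves 34 controls.

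Suppose hyaluronidase takes a treated participant's change from the assumed 1.1 mL to 0.2 mL (the control mean) or to 0, and the participant exits before the Week 24 window opens at Day 142. Leaving that value out raises the treated mean by:
- 0.9/102 = 0.009 mL to 1.1/102 = 0.011 mL with the full 15% attrition by Week 24;
- 0.9/120 = 0.008 mL to 1.1/120 = 0.009 mL with none.

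If the exit image is the one selected in the Week 8 or Week 16 window, the model carries part of the fall forward. Assumed within-participant correlations of 0.5 to 0.8 (compound symmetry or AR(1)) put a weight of 0.25 to 0.80 on that image. The effect is then (1 − 0.80) × 0.0088 = 0.002 to (1 − 0.25) × 0.0108 = 0.008 mL.

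**4. Power if these participants are kept and counted as observed**

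Of 102 treated, k have a change of 0 (k is an assumption). With p = k/102, the difference is 0.9 − 1.1p and the treated SD is √(0.81 + 1.21p(1 − p)). Pooled t-test against 34 controls with SD 0.9:

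| k | Difference (mL) | Power |
|---|---|---|
| 0 | 0.900 | 99.9% |
| 1 | 0.889 | 99.8% |
| 3 | 0.868 | 99.7% |
| 6 | 0.835 | 99.5% |
| 12 | 0.771 | 98.2% |

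**5. Outside filler in an untreated control**

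For a retained control with 0.9 mL of outside filler (assumption; range 0.5 to 3.0), the control mean at Week 24 would rise by up to 0.9/34 = 0.026 mL (0.5/34 = 0.015 to 3.0/34 = 0.088). Withdrawal under 6.6 limits this.

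**The case against.** Hyaluronidase and outside fillers are prohibited, so 6.6 governs only breaches and emergencies, and the number of cases may be zero. The gravest cases are largely covered: hyaluronidase given to prevent permanent impairment meets the SAE definition in 11.1.2, and 11.4 then requires follow-up to outcome. On this view the rule is a legitimate design choice that needs no change. Much of this stands, and it is why the priority is low. What it does not supply is a scheduled visit, or routine in-trial recording of a new non-serious AE, after exit.

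A second objection is that retention brings altered data into the analyses. Post-event GAIS and NSS scores would enter the as-observed responder analyses (SAP 5.4.2), not just the images. This stands, so the fix has to cover all three measures. Case-by-case review under Protocol 10.2 ("The use of the data collected for the subject will be discussed to determine if the data are to be included in the analysis") and the PP analysis help, but neither sets a rule in advance for the primary mITT analysis.

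A reader might infer that 6.6 contradicts its own pregnancy rule. It does not: both products act on the nose and pregnancy does not. The pregnancy sentence matters only as wording already in use.

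A reader might also infer that every such participant should be retained, including untreated controls who receive an outside filler. The documents do not support that. The long-term purpose in 4.1 concerns people who received the device, and keeping such controls would bring filler-altered volumes into the Week 24 window.

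**Conclusion.** The point holds for study-treated participants given hyaluronidase: 6.6 ends visits and routine recording of new non-serious AEs that the trial could keep at little cost. It is weaker for a study-treated participant given an outside filler, because later AEs are harder to attribute.

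The loss is at most 39.6 weeks for a treatment-group event at Day 60 (24.0 to 47.1 weeks for events from Day 169 back to Day 7), in a number of participants that the documents do not allow to be estimated. The primary estimate moves by about 0.01 mL per treated participant, in favour of the device, on the planning means and an assumed fall to between 0.2 mL and 0. A reader might infer that the primary result is at risk. It is not: with six such participants kept and counted at zero change, power is still 99.5%.

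The visible SAP text names neither event, and its intercurrent-event entry (SAP 1.1) deals only with missing data. Some sections are not in the public text, so nothing firmer is claimed there.

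**What to change.** **Protocol 6.6.** A study-treated participant who receives hyaluronidase gets no further study treatment but stays on the visit schedule for everything other than injection, as the section already provides for pregnancy. Record the product and date. The same may apply, for safety visits, to a study-treated participant who receives an outside nasal filler. An untreated control who receives an outside filler is still withdrawn. When hyaluronidase may be given does not change. Align the exit-visit wording in 6.2.3.1, 6.2.3.2 and 6.5.

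**SAP 1.1, 5.3 and 5.4.** State that images, GAIS and NSS scores after hyaluronidase are used as observed, and that those after an outside filler are excluded from the primary and responder analyses. Fix this before the data are seen.

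**Cost.** A short protocol amendment and a few SAP lines. The visits are already scheduled and concomitant procedures already recorded; a participant with a Day 60 event would attend four visits instead of one exit visit. Some participants will decline, and AEs after an outside filler will remain hard to attribute.
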